### **3 Investigational Plan**

#### **3.1 Study Design**

This is a randomized, double-blind, placebo-controlled, 4-arm, parallel-group, proof-of-concept, and dose-finding adaptive Phase 2a/2b study.

Approximately 100 sites will participate in the study; approximately 75 in the European Union and approximately 25 in the United States and Canada. Participating sites will be required to adhere to the Surviving Sepsis Campaign 2012 (Delinger et al 2013) and KDIGO® (Kidney Disease: Improving Global Outcomes) Clinical Practice Guideline for AKI recommendations (KDIGO Acute Kidney Working Group 2012).

A minimum of 290 patients with SA-AKI will be enrolled in the study. The study involves 2 parts (Part 1, Part 2) with an interim analysis between the parts, with continued recruitment during this interim analysis. Of the 290 planned patients, at least 120 patients will enroll in Part 1 and 170 patients will enroll in Part 2 with an estimated 50 patients during the interim analysis. Patients enrolled during Part 1 and interim analysis will be randomly assigned to receive, by 1-hour IV infusion, either placebo (Part 1; n1 = 30) or one of 3 different doses of recAP (Part 1; n1 = 30 in each dosing arm; i.e., 0.4 mg/kg [250 U/kg], or 0.8 mg/kg [500 U/kg], or 1.6 mg/kg [1000 U/kg]) using a 1:1:1:1 allocation ratio. Patients will receive study drug by 1-hour IV infusion once daily for 3 days (Days 1, 2, and 3). The interim analysis on the primary endpoint will be performed on all the data collected after the 120th patient of Part 1 has completed the Day 7 visit of the study to select the dose to be administered in Part 2. The dose chosen will be the optimal dose of recAP on the primary endpoint in Part 1, provided there are no safety issues with that dose as judged by the data monitoring committee (DMC). In Part 2, patients will be randomly assigned to receive, by 1-

[figure not shown]
hour IV infusion, either placebo ( $n_2 = 85$ ) or the dose of recAP ( $n_2 = 85$ ) selected during the interim analysis. Patients recruited during the interim analysis period to the dose selected in Part 2 will form part of the Part 2 populations, but those recruited to the doses that are not selected will be included in the Part 1 population.

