Efficacy endpoints will be summarized for all four treatment groups excluding patients recruited whilst the interim analysis is performed to treatment arms not selected for Part 2. Any analyses of the other efficacy endpoints will compare the optimal recAP dose and placebo treatment groups only. All safety data will be summarized for all four treatment

groups including patients recruited at any point in the study. Similarly, all data listings will include patients recruited at any point in the study.

See also [Section 4.3](#) for definitions of the analysis sets used in the study, which also state which patients (i.e. recruited during Part 1, or recruited during Part 2) are included in each analysis set.

Display of data

Continuous variables will be summarized using descriptive statistics, including but not limited to the mean, standard deviation, median, lower quartile, upper quartile, minimum value, and maximum value. For the summary statistics of all numerical variables minimum and maximum will be displayed to the same level of precision as reported, unless otherwise specified. Mean, median, lower quartile and upper quartile will be displayed to one level of precision greater than the data collected. Standard deviation / standard error will be displayed to two levels of precision greater than the data collected. P-values will be rounded to three decimal places. If a p-value is less than 0.001 it will be reported as “<0.001.” If a p-value is greater than 0.999 it will be reported as “>0.999”.

Categorical variables will be summarized using frequency counts and percentages. When count data are presented, the percentage will be suppressed if the count is zero in order to draw attention to the non-zero counts. The denominator for all percentages will be the number of patients in that treatment within the analysis set of interest, unless otherwise specified. All percentages will be presented to one decimal place. Categorical summaries will display all categories available on the electronic case report form (eCRF). A row denoted “Missing” will be included in count tabulations only when information is missing for a categorical variable.

All data summaries will be provided by treatment arm.

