4.1. Sample Size

A sample size of $n_1 = 30$ patients per treatment group in Part 1 with an additional $n_2 = 85$ patients recruited to each of the optimal recAP dose and placebo treatment groups in Part 2 (for a total sample size of $n = 290$ patients) is planned. Recruitment will continue during the interim analysis, so the total number of patients will exceed 290. Custom programmed simulations were performed using SAS[®] Version 9.2 (SAS Institute, Inc, Cary, North Carolina) to determine power and type I error rate of the chosen sample size and design under a number of different dose response scenarios. Each scenario assumed a standard deviation of 49 mL/min for the primary endpoint (area under the time-corrected endogenous creatinine clearance curve from Day 1 to Day 7 [AUC₁₋₇]) with an assumed response of 60 mL/min for the placebo group, and between 60 mL/min (no treatment effect) and 79 mL/min (strong treatment effect) for the recAP dose groups.

Fifty-thousand simulations were performed to show that the 1-sided type I error rate is 2.4% (and hence is well controlled at the 1-sided 2.5% significance level). The power was defined as the probability of rejecting the null hypothesis (of no difference between treatment groups) when 1 or more recAP dose groups have an effective treatment effect, defined as a response of 69.5 mL/min. This was investigated across 7 scenarios with 10 000 simulations performed for each. In the most realistic scenarios (with strong treatment effects, i.e., responses of 79 mL/min for the medium and high recAP dose groups and a varying response of between 60 mL/min and 79 mL/min for the low-dose group) the chosen design achieved power of between 79% and 86%. This dropped to 66% to 67% for other scenarios where only the high recAP dose group had a strong treatment effect.

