6.4. Inclusion and Exclusion Criteria

A listing, based on the all Enrolled Set, will be included displaying which protocol version/amendment each patient was recruited under, and whether the patient met and/or did not meet the inclusion and exclusion criteria.

7. Treatments and Medications

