8.1.1. Primary Analysis

The primary efficacy analysis will be an analysis of variance (ANOVA) of the area under the time-corrected endogenous creatinine clearance curve from Day 1 to Day 7 with treatment and site as explanatory variables.

For all patients recruited up to the interim analysis, the primary efficacy analysis will be conducted for the ITT Combined Set at the interim analysis (which is identical to the ITT Part 1 Interim set at the time of the interim analysis) where AUC_{1-7} will be compared between the 3 active treatment groups and placebo. This analysis will be considered in conjunction with the safety data to determine the optimal recAP dose for use in Part 2.

The primary efficacy analysis will be conducted for the ITT Part 2 Set, PP Day 1 – 7 Part 1 and PP Day 1 – 7 Part 2 Set where AUC_{1-7} will be compared between the optimal recAP dose and placebo (for the PP Day 1 -7 Combined Set, each dose of recAP will be compared to Placebo). Also, all doses combined will be compared to Placebo.

Confirmatory testing of the single hypothesis comparing optimal dose with placebo will be based on a closed-testing procedure. This hypothesis will be rejected at the 5% significant level if it and all intersection hypotheses involving it are all rejected at the 5% significance level. The testing strategy used to combine results from Parts 1 and 2 will be a combination test based on the inverse normal method, with the test statistic of the combination test calculated as ([Bauer and Köhne 1994](#)):

$$\sqrt{\frac{n_1}{n}} \Phi^{-1}(1 - p_1) + \sqrt{\frac{n_2}{n}} \Phi^{-1}(1 - p_2)$$

where n_1 and n_2 are the sample sizes per group in interim analysis at Part 1 and in Part 2, respectively, $n = n_1 + n_2$, Φ refers to the standard normal distribution, and p_1 and p_2 are the one-sided p-values from interim analysis at Part 1 and from Part 2, respectively. For the intersection hypotheses, p_1 is the Dunnett adjusted one-sided p-value in Part 1 (for the optimal dose selected), and p_2 is the one-sided unadjusted p-value to compare optimal dose with placebo in Part 2 for all hypotheses.

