Kidney function will be assessed at Baseline, Day 14, 21 and 28 by measured creatinine clearance. Baseline kidney function will only be measured by standardized creatinine clearance, however for Day 14, 21 and 28 summaries if creatinine clearance is not available then kidney function as assessed by eGFR (estimated by the CKD-EPI formula based on serum creatinine) will be used.. Kidney function will also be assessed at Day 60 and Day 90 by eGFR. Sustained loss of Kidney function, defined by eGFR < 60 mL/min, will be assessed at Day 60 and Day 90. The analyses of kidney function and sustained loss of kidney function at each timepoint will exclude any patients who die prior to the timepoint. Any other missing assessments (including early withdrawals) at Day 60 or Day 90 will be imputed by LOCF where possible, missing Day 14, 21 and 28 values will not be imputed and will be treated as missing. A summary table will present descriptive statistics for the reference kidney function and the kidney function at Baseline and at Days 14, 21, 28, 60 and 90 along with counts and percentages of patients with loss of sustained kidney function at Day 60 and Day 90. Descriptive statistics will also be presented for the change from baseline creatinine clearance value at Day 14, Day 21, Day 28, Day 60, and Day 90.

The absolute difference between placebo and each of the treatment groups will also be presented at each time point. Summaries for Day 60 and 90 will be repeated with and without the LOCF imputation of missing values applied.

All kidney function data will be listed.

Dialysis Dependency

Incidence of dialysis dependency will be assessed at Day 60 and Day 90. Patients who die or withdraw from the study prior to Day 60 or Day 90, respectively, without recording incidence of chronic dialysis will be counted as not being dialysis dependent. A summary table will present the counts and percentages of patients who are dialysis dependent at Day 60 and Day 90. Percentages for each timepoint are calculated based on the number of patients that were assessed including those who died or withdrew prior to timepoint.

All data on dialysis dependency will be listed.

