Secondary Efficacy Endpoints (Section 8.2)	Contrary to Section 7.7.2 of the protocol, two sets of outputs have not been produced for these endpoints. Instead, the planned summaries have been combined to present all four treatments for all patients (i.e., per the safety analysis).
Other Secondary Endpoints (Sections 3.2.3 and 8.2.2.1)	Kidney function at Days 14 and 21 will also assessed and analyzed.
Other Endpoints (Sections 3.2.4)	Total time in ICU/Intermediate care and Total time in hospital also based on time to decision of transfer.
Other Endpoints (Section 3.2.4)	Total time in ICU/Intermediate care and Total time in hospital, based on time to decision of transfer deleted.

13. Change History

Version (date)	Section	Summary of change
1.4 (06DEC2016)	2.3	FE Urea analysis added
1.4 (06DEC2016)	3.1	Schedule of events – treatment administration updated to be within 96 hrs from sepsis first diagnosis
1.4 (06DEC2016)	3.2.3	Added BUN/Urea clearance as other secondary endpoint
1.4 (06DEC2016)	3.2.3	Added kidney function assessment at Day 14, 21 and 28 as other secondary endpoint
1.4 (06DEC2016)	3.2.3	Added incidence of dialysis dependency at Day 60 and Day 90 as other secondary endpoint
1.4 (06DEC2016)	4	Added information on the assignment of patients to analysis sets who were recruited during the interim analysis
1.4 (06DEC2016)	4	Added information that all summaries will be provided by treatment arm
1.4 (06DEC2016)	4	Updated ‘average dose received’ and ‘received treatment group assignment’ categories
1.4 (06DEC2016)	4.3.2.2	ITT Part 1 Interim analysis set added
1.4 (06DEC2016)	4.3.2.2	PP Day 1 – 7 Part 1 analysis set added
1.4 (06DEC2016)	4.3.6	Iohexol analysis set added
1.4 (06DEC2016)	6.2	Acute physiology and chronic health evaluation (APACHE II) score added to baseline disease characteristics

Version (date)	Section	Summary of change
1.4 (06DEC2016)	6.2	Number and percentage of patients with vasopressor/inotropic therapy use added to baseline disease characteristics
1.4 (06DEC2016)	6.2	FE Urea added and creatinine clearance is using formula given in 8.1 section and CKD-EPI formula added in the appendix.
1.4 (06DEC2016)	8	Supportive analysis updated to include specific group categories as factors.
1.4 (06DEC2016)	8	Table added to provide an overall summary of the efficacy analyses
1.4 (06DEC2016)	8.1	Updated so only adjudicated Part 1 will be used in sensitivity analysis.

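### Two dropped recAP doses are set against placebo pooled over both parts, about 63% of it randomised after those doses close, with no term for part or period

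*SAP*

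**What the plan says.** **Enrolment.** Protocol 3.1 randomises patients 1:1:1:1, in Part 1 and during the interim analysis, to "either placebo (Part 1; n1 = 30) or one of 3 different doses of recAP". SAP 4.1 adds 85 "patients recruited to each of the optimal recAP dose and placebo treatment groups in Part 2". Protocol 3.1 expects that "170 patients will enroll in Part 2 with an estimated 50 patients during the interim analysis". Under Protocol 5.1 and SAP 4.2 the codes for the two non-selected doses are withdrawn once the dose is chosen.

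**Interim-period patients.** SAP 4 counts those on placebo or the selected dose in Part 2. Those on the other doses are left out of efficacy, apart from one sensitivity analysis of the primary endpoint, but stay in safety.

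**Pooled displays and contrasts.**
- SAP 8.1.1, PP Day 1-7 Combined Set: "each dose of recAP will be compared to Placebo). Also, all doses combined will be compared to Placebo". The model terms are treatment and site. The sentence on all doses combined does not name its analysis set.
- SAP 8.2.2.1, kidney function, on the ITT Combined Set (per 8.2.2): "The absolute difference between placebo and each of the treatment groups will also be presented at each time point".
- SAP 12, Table 12-1, secondary endpoints: "Instead, the planned summaries have been combined to present all four treatments for all patients".
- SAP 4, safety: tables cover all four "groups including patients recruited at any point in the study".

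**Checks.** SAP 4 treats a common patient population across parts as an assumption and repeats baseline data by part for the selected dose and placebo. SAP 6.1 and 6.2 give baseline tables for ITT Part 1 and ITT Part 2. SAP 6.4 plans a listing "displaying which protocol version/amendment each patient was recruited under".

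**The concern.** Nobody is randomised to a dropped dose after the dose decision, whereas most placebo patients are. If case mix, care or measurement changes over time, pooled placebo reflects mainly the later period and the dropped doses only the earlier one. The change then enters the dose-placebo difference, in either direction.

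The confirmatory test is protected because it combines p-values calculated within each part. The outputs listed above have no such protection. One of the two primary objectives is to identify the dose or doses for Phase 3, so a reader of the final report will look at all three doses beside placebo for kidney function, mortality and safety. For two of the three, that comparison is largely non-concurrent.

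The documents give some reason to expect differences over time. Amendment 2 raised the number of sites from about 50 to about 100 and widened eligibility. AUC1-7 is also processed differently by part: SAP 8.1 uses adjudicated values for Part 2 but keeps adjudicated Part 1 values for a sensitivity analysis, and the SAP does not say which Part 1 values enter the PP Combined comparison.

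**Working it through.** **Inputs.** n1 = 30 per arm and n2 = 85 per arm (Protocol 3.1, SAP 4.1); about 50 interim-period patients at 1:1:1:1 (Protocol 3.1), so 50/4 = 12.5 per arm; SD 49 mL/min, placebo mean 60, effective response 69.5 (SAP 4.1); two-sided 5% tests (SAP 4). The drift sizes are assumptions, because the documents give none.

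**The plan's own figures.** A simulation of the stated design (best Part 1 mean selected, Dunnett-adjusted intersection test, inverse-normal weights, futility rule, no site effect) gives power of 85.5%, 79.2% and 81.4% with the medium and high doses at 79 and the low dose at 79, 69.5 and 60. The plan states 79% to 86%. With only the high dose at 79 it gives 65.7% (other doses 69.5/69.5) and 67.2% (60/69.5), against 66% to 67%; a 60/60/79 profile gives 69.4%. Type I error is 2.46% against 2.4%. The inputs are therefore read correctly.

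**Make-up of placebo.**
- Part 2 label: 85/(30 + 85) = 73.9%.
- Randomised after closure: (85 − 12.5)/115 = 63.0%. With 30 to 70 interim-period patients this is 67.4% to 58.7%.
- If interim-period placebo patients come on top of the 85: 85/127.5 = 67% after closure, and 97.5/127.5 = 76% labelled Part 2.

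**Bias of a dropped-dose efficacy contrast (30 vs 115).** Bias = late share of placebo × d, because the dropped dose has no late patients. A step at closure gives 0.63d; a step at the Part 2 label gives 0.74d.

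SE = 49 × √(1/30 + 1/115) = 10.05. The rejection rate under no drug effect is P(|Z + bias/SE| > 1.96).

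| d (mL/min) | bias, step at closure | rate | bias, step at label | rate |
|---|---|---|---|---|
| 5 | 3.2 | 6.1% | 3.7 | 6.6% |
| 10 | 6.3 | 9.6% | 7.4 | 11.4% |
| 15 | 9.5 | 15.6% | 11.1 | 19.7% |

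For scale, the plan's effective difference is 69.5 − 60 = 9.5 mL/min.

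**All doses combined (175 vs 115).** Step at the label: 85/115 − 85/175 = 0.739 − 0.486 = 0.25d. Step at closure: 72.5/115 − 72.5/175 = 0.630 − 0.414 = 0.22d. With d = 10, the bias is at most 2.5 and SE = 49 × √(1/175 + 1/115) = 5.88, so the rate is about 7%.

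**Safety tables.** Interim-period patients on dropped doses are kept here, so a dropped arm has about 30 + 12.5 = 42.5 patients. Suppose mortality were 30% before closure and 20% after, with no drug effect. Pooled placebo would show (42.5 × 0.30 + 72.5 × 0.20)/115 = 23.7%, an apparent excess of 6.3 points on each dropped dose. If the step came at the start of the interim period, the multiplier would be 85/115 − 12.5/42.5 = 0.739 − 0.294 = 0.45.

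**The case against.** The strongest reply is that little depends on these outputs. Dose selection uses the interim ANOVA, in which all four arms are concurrent. The confirmatory test is built from within-part p-values. The PP analysis is supplementary (SAP 8.1.1), and SAP 4 limits analyses of the other efficacy endpoints to the selected dose against placebo. The mortality test and the composite-endpoint models never test a dropped dose. All of this stands, and it limits the point to one supplementary set of contrasts and to descriptive columns.

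It is also fair that a careful reader could detect drift. Baseline tables are given by part, and AUC1-7 and RRT incidence are reported for ITT Part 1 Interim and ITT Part 2 separately. The site term would absorb drift caused by a changing mix of sites, but not change within a site, and the safety tables have no adjustment. SAP 9 says safety is presented for both parts, which might mean by part, but the wording in SAP 4 reads as pooled.

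Three stronger readings might be inferred, and the documents do not support them:
- *Three-quarters of placebo enrolled after the doses closed.* Part 2 includes about 12 or 13 placebo patients randomised alongside the dropped doses, so the figure is about 63%.
- *No concurrent four-arm safety data exist.* SAP 11 lists four-arm adverse events, causes of death, laboratory results and vital signs at the interim analysis. That is an early cut with incomplete follow-up, but it exists.
- *The dropped doses are confounded with eligibility version.* Amendment 2 describes Part 1 enrolment and the interim analysis prospectively. The documents do not show how protocol versions split between parts, so the change may fall within Part 1 and affect all arms alike.

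**Conclusion.** The point holds for the PP Day 1-7 Combined contrasts of non-selected doses with placebo, the kidney-function differences, and the final four-arm safety and secondary tables. In these outputs between-period drift passes into a dropped-dose efficacy contrast at about 0.63 to 0.74 of its size, and nothing in the specification removes within-site change. For all doses combined the fraction is only about a quarter.

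No concurrent four-arm final table is specified for safety, mortality or kidney function. Concurrent four-arm output is specified for AUC1-7, RRT and the interim safety cut.

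This is an inexpensive improvement to supplementary and descriptive output; it does not challenge the primary result. The sizes assume step drift, an equal split of about 50 interim-period patients, interim placebo counted within the 85, planned numbers without PP exclusions, and no adjustment by site. The documents do not show that drift occurs.

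**What to change.** **Modelled contrasts (SAP 8.1.1).** For any non-selected dose, and for all doses combined, either restrict the comparison to concurrently randomised patients or add a term for randomisation before or after dose closure. Name the analysis set for the all-doses comparison.

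**Displays (SAP 8.2.2, 8.3 and 9).** For kidney-function differences and the final safety, mortality and secondary tables, show non-selected doses beside placebo randomised while all four arms were open. Keep pooled Part 1 + Part 2 columns for the selected dose and placebo. State in SAP 9 whether safety is shown by part.

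**Cost.** SAP wording, one population flag and some precision. The SE of the AUC1-7 difference, now 10.05 (30 vs 115), becomes:
- 49 × √(1/30 + 1/42.5) = 11.7 with all placebo randomised before closure, under the present exclusion of interim-period patients on non-selected doses;
- 49 × √(2/30) = 12.65 with Part 1 patients only;
- 49 × √(2/42.5) = 10.6 if SAP 4 and 4.3.2 are also changed to admit those interim-period patients to these efficacy contrasts.

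The first option removes a step at closure, but a step at the start of the interim period would leave 12.5/42.5 = 0.29d. The other two remove both.
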